1.6 SAMPLING METHOD

Consecutive sampling was used until the sample size was attained.

1.7 SAMPLING PROCEDURE

Patients 18 years or older that had been admitted for either elective or emergency surgery under regional anaesthesia were selected while in the pre-operative waiting area. Screening for eligibility was done by the principal investigator or by the research assistants. Patients that met the eligibility criteria were then consented and enrolled into the study. Patient data was gathered using a pretested questionnaire that included age, sex, medical history, anaesthetic technique used, duration of surgery, intraoperative medication and any nausea or vomiting within 24hours of surgery. Patients were followed up for up to 24 hours post-operatively.

1.8 DATA MANAGEMENT

1.8.1 DATA COLLECTION

A standardised questionnaire was completed by the study research assistants or the principal investigator during the immediate pre-operative period to assess pre-operative risk of post-operative nausea and vomiting. The information collected included patient demographics, past medical history, information on fasting and co-morbidities. A second questionnaire was used to assess the perioperative conduct of anaesthesia and any events occurring within this period. It contained the follow up information as well.

Patients were followed up once at 24 hours to assess for post-operative nausea and vomiting.

1.8.2 INDEPENDENT VARIABLES:

Socio demographic data such as age and sex, the diagnosis and type of procedure, ASA classification, history of PONV or motion sickness, non-smokers, peri-operative opioid use, period of pre-operative fasting, PONV prophylaxis use, duration of anaesthesia and surgery were studied.

1.8.3 DEPENDENT VARIABLE:

Post-operative nausea and vomiting measured by any retching, nausea or vomiting within 24 hours following surgery under regional anaesthesia.

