1.8.4 DATA ANALYSIS AND SAFETY

Completeness and accuracy of data was checked daily and organised by the principal investigator before storage. Data was double entered into the computer using EPI data version 3.1, and then subsequently exported to STATA version 14.0 for analysis.

Analysis was done using STATA with the help of a statistician. Both raw data and the analysed form were kept both electronically and hardcopy for further reference.

All questionnaires were stored in a secure, waterproof place to enable confidentiality and were only available to the principal investigator.

Participant characteristics were expressed as categorical and/or continuous variables.

Continuous variables were expressed as means and standard deviations while categorical data was expressed as frequencies with their respective proportions. Data presentation is in tabular and graphic forms.

Cumulative incidence was assessed as the proportion of study participants who developed PONV within 24 hours of follow up divided by the total number of study participants enrolled into the study with complete follow up.

At the bivariate level, each variable was compared with the outcome variable using cross tabulation and the logistic analysis. Variables that had p-value less than 0.200 at bivariate analysis were considered for multivariate analysis using logistic regression and variables were considered significant if the p-value <0.05.

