1.8.5 QUALITY CONTROL AND ASSURANCE

Pre-testing of the questionnaires was done on non-study participants and changes made to the questions where necessary before final data collection.

Translation of the consent form into Luganda, the main local language used in Mulago was done prior to the start of data collection.

Research assistants were trained on how to obtain informed consent, patient approach and proper data collection before data collection commenced.

All questionnaires were safely stored to enable revisiting them when necessary.

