5.3 Type of feeds (tick)		
Solids semi-solids	liquids	

Study Number: Patient's name: 1. Anaesthesia provider (Tick) 1.2 AO 1.3 SHO 1.1 AO student trainee 1.4Anaesthesiologist 2. Length of the operation 2.1 Time surgery i) started...... ii) ended (state in 24hour clock) 2.2 Duration of anaesthesia 30 min L 30-60min 60-120min >120min 2.3 Duration of surgery 30 min ____ 30-60min 60-120min >120min 3. Conduct of anaesthesia and surgery 3.1. Type of Surgery Emergency Elective 3.2. Anaesthetic technique (state)

1=Yes

2=No

QUESTIONNAIRE 2

Sedation used

3.3. Number of attempts at the block(tick) 1	2	>2
3.4.Drugs used during anaesthesia(tick)		
o. i.Di ugo useu during anaestnesia(tiek)	1=Yes	2=No
	1–1 es	2-110
Opioids		
If yes, state which opioid	••••	
Anti-emetics		
If yes, state which anti-emetic		
Sedatives		
If yes, state which sedative		
3.5.Did any of the following happen duri	ng surgery? (Tick aj	opropriately)
	1=Yes	2=No
Retching		
Nausea		
Vomiting		
3.6.Lowest BP recorded(tick)		
SBP <110 <90	<50	
DBP <90 <70	<50	

4. Recovery room

[figure not shown]

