5.1 Did any of the following happen during recovery? (Tick appropriately)

	1=Yes	2=No
D . 11		
Retching		
Nausea		
rvausca		
Vomiting		

5. At 24 hours (tick)

5.1 Nausea or vomiting 1= Yes 2=No 5.2 If yes, time to occurrence of PONV from time of surgery.....hours.....min

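### PONV is defined to include retching for 24 hours, but the 24-hour item asks only about nausea or vomiting, so late retching alone may be counted as PONV-free

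*Protocol*

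**What the plan says.** Protocol section 1.8.3 gives the dependent variable as "Post-operative nausea and vomiting measured by any retching, nausea or vomiting within 24 hours following surgery under regional anaesthesia": three symptoms, any one of which qualifies, over one 24-hour window.

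Questionnaire 2 asks about symptoms in three blocks:

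- **During surgery** (item 3.5, opening "3.5.Did any of the following happen"): separate yes/no rows for retching, nausea and vomiting.
- **Recovery room** ("Did any of the following happen during recovery"): the same three rows.
- **At 24 hours**: one combined item, "5.1 Nausea or vomiting 1= Yes 2=No". Item 5.2 follows with "If yes, time to occurrence of PONV from time of surgery".

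Section 1.8.1 provides for one follow-up contact, at 24 hours. Section 1.7, describing what the questionnaire collects, also names nausea and vomiting over 24 hours without retching. Section 1.8.4 builds the cumulative incidence on "the proportion of study participants who developed PONV within 24 hours of follow up".

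**The concern.** The definition and the collection form in the same document do not match. The form lists retching separately from nausea and from vomiting in two blocks, so an interviewer following it has reason to treat retching as a distinct symptom. In the third block, which covers most of the risk period, retching is not named.

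Objective 1 is at stake. If a participant with late retching alone is recorded as a no at 24 hours, the numerator loses a case that meets 1.8.3. The error runs one way: it can lower the incidence of the outcome as defined but cannot raise it. The outcome would also have three components in recovery and two at the 24-hour contact, so the reported figure would not carry the meaning that 1.8.3 gives it. The effect on the associations in objective 2 is likely small.

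An analysis plan could not repair this, because it cannot recover an event that was never recorded.

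**Working it through.** **Definition against form**

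| Period | Counts under 1.8.3? | Retching on the form | Nausea, vomiting on the form |
|---|---|---|---|
| During surgery (item 3.5) | No, not postoperative | Own row | Own rows |
| Recovery room | Yes | Own row | Own rows |
| After recovery to 24 hours | Yes | Not named | One combined item |

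The gap is confined to retching after recovery with no nausea or vomiting at any time after surgery and no retching in recovery. A participant with late retching plus nausea or vomiting is still counted.

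The protocol does not say how the rows are combined. I assume PONV is any yes in the recovery rows or the 24-hour item. Whether the 24-hour item covers all 24 hours or only the time after recovery does not matter under this rule, since the union is the same.

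**Planning figure reproduced (section 1.5, objective 1)**

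Inputs: Z = 1.96, P = 0.314, D = 0.05.

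N = Z² P(1 − P) / D² = 3.8416 × 0.314 × 0.686 / 0.0025 = 330.998, so the stated 331 reproduces. With the 10% addition, 331 × 1.10 = 364.1, so 364 also reproduces.

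**Illustrative size of the undercount**

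Expected cases among 331 participants: 331 × 0.314 = 103.9.

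Let r be the share of all cases that are late retching alone and are recorded as a no. Recorded incidence = P(1 − r); shortfall = P × r. The documents give no r, so every value below is an assumption.

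| r | Cases missed | Recorded incidence | Shortfall |
|---|---|---|---|
| 1% | 103.9 × 0.01 = 1.0 | 31.4 × 0.99 = 31.1% | 0.3 points |
| 5% | 103.9 × 0.05 = 5.2 | 31.4 × 0.95 = 29.8% | 1.6 points |
| 10% | 103.9 × 0.10 = 10.4 | 31.4 × 0.90 = 28.3% | 3.1 points |

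Share needed for the shortfall to equal the planned 5-point error: 5 / 31.4 = 15.9% of cases, or 0.05 × 331 = 16.6 participants.

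Section 1.5 uses a lower overall proportion for objective 2, P = 0.114. There, expected cases are 331 × 0.114 = 37.7. At r = 1% the recorded incidence is 11.4 × 0.99 = 11.3% (shortfall 0.1 points). At r = 10% it is 11.4 × 0.90 = 10.3% (3.8 cases missed, shortfall 1.1 points).

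**The case against.** The best defence is that the protocol uses nausea or vomiting as shorthand for PONV. Section 1.7 summarises the questionnaire that way although the same questionnaire has a retching row in recovery. Section 1.8.1 says the 24-hour contact was to assess PONV, the term that 1.8.3 defines to include retching. Item 5.2 calls a yes PONV. On this reading interviewers may have ticked yes for retching alone. Section 1.8.5 adds that the questionnaires were pre-tested and altered where needed, without saying whether the printed form is the version before or after. It also says "Research assistants were trained on how to obtain informed consent, patient approach and proper data collection before data collection commenced".

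This stands as a caution about what was actually collected, and it is why the conclusion says that cases may have been missed. It does not remove the mismatch: the separate rows elsewhere favour the stricter reading, and the protocol's account of the training does not mention retching.

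Two further points are fair. The size cannot be found from the documents, and section 1.5 does not say whether the study behind the 31.4% counted retching, so the figures above are illustrative. And a sensitivity definition restricted to nausea or vomiting cannot recover or bound missed late retching. It can only equal or lower the incidence, so its value is consistency across the two windows.

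**Conclusion.** The point holds, as a minor one. The mismatch between 1.8.3 and the 24-hour item is certain on the face of the protocol. Whether incidence was undercounted, and by how much, is not known.

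The conclusion rests on two assumptions: that PONV is any yes in recovery or at 24 hours, and that interviewers did not record retching under the 24-hour item. If both hold, any bias in objective 1 is downward. Over the assumed range of 1% to 10% of cases it stays inside the planned 5-point error at either of the protocol's overall proportions. The sample size is not called into question.

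**What to change.** **If data are already collected**, as the past tense and the dates August 2018 to January 2019 indicate:

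1. Restate 1.8.3 to match the form: retching, nausea or vomiting in recovery, or nausea or vomiting reported at the 24-hour contact, with PONV as any yes in either. If interviewers did record retching under the 24-hour item, say so there instead.
2. Report nausea or vomiting in both windows as a sensitivity definition, labelled as a consistency check and not as a correction for missed cases.
3. State as a limitation that incidence under 1.8.3 as now written may be understated.

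The number of retching-only cases in recovery can be counted, since "All questionnaires were safely stored to enable revisiting them when necessary". It is a rough indication only, because it need not carry over to the later period.

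Cost: one restated definition, one estimate from rows already recorded and one sentence. No new data are needed.

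**If the form is still in use**, replace the combined 24-hour item with three rows (retching, nausea, vomiting) and define PONV as any yes in the recovery or 24-hour rows. Cost: three tick rows in place of one item, at a contact that already takes place.

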1.8.4 DATA ANALYSIS AND SAFETY

Completeness and accuracy of data was checked daily and organised by the principal investigator before storage. Data was double entered into the computer using EPI data version 3.1, and then subsequently exported to STATA version 14.0 for analysis.

Analysis was done using STATA with the help of a statistician. Both raw data and the analysed form were kept both electronically and hardcopy for further reference.

All questionnaires were stored in a secure, waterproof place to enable confidentiality and were only available to the principal investigator.

Participant characteristics were expressed as categorical and/or continuous variables.

Continuous variables were expressed as means and standard deviations while categorical data was expressed as frequencies with their respective proportions. Data presentation is in tabular and graphic forms.

Cumulative incidence was assessed as the proportion of study participants who developed PONV within 24 hours of follow up divided by the total number of study participants enrolled into the study with complete follow up.

At the bivariate level, each variable was compared with the outcome variable using cross tabulation and the logistic analysis. Variables that had p-value less than 0.200 at bivariate analysis were considered for multivariate analysis using logistic regression and variables were considered significant if the p-value <0.05.

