1.5 SAMPLE SIZE CALCULATION

Objective 1

Assuming an incidence of PONV in regional anaesthesia of 31.4%(Quinn et al., 1994) with an absolute error of 0.05 and 95% CI

Using Kish Leslie formula:

$$N = Z^2 P (1-P)$$

 D^2

Where N=sample size required to determine incidence

Z is the value corresponding to 95% confidence interval=1.96

P is the prevalence of PONV among patients undergoing surgery under regional anaesthesia=0.314 from previous studies

D is the absolute error=0.05

$$N = 1.96 \times 1.96 \times 0.314 (1 - 0.314)$$

 0.05×0.05

N = 331 patients

Adjusting for loss to follow up of 10%

$$N = n (100+10)/100$$

=331(100+10)/100

=364 patients

Objective 2

From the comparison of two proportions formula:

$$N = \frac{\left(Z\alpha\sqrt{\left(\frac{1}{q1} + \frac{1}{q2}\right)P(1-P)} + Z\beta\sqrt{P1(1-P1)\frac{1}{q1} + P2(1-P2)\frac{1}{q2}}\right)^2}{(P1-P2)^2}$$

Using the factor of gender for PONV in regional anaesthesia according to a study by AC Quinn et al 1994

q1 is proportion of males in study =336/606=0.554

q2 is proportion of females in study =270/606=0.446

p1 is proportion of males with PONV =22/336 =0.065

p2 is proportion of females with PONV =47/270 = 0.174

 $P=p1q1+p2q2=(0.065x0.554+0.174x0.446)=0.03601+0.0776=0.1136\sim0.114$

 $Z\alpha$ is standard normal corresponding to level of significance. Using a level of significance of 5%, $Z\alpha$ = 1.96

 $Z\beta$ corresponds to power of the study. For a power of 80% $Z\beta$ = 0.841

N=272patients

Therefore, choosing the larger sample size from the calculation for sample size for the first objective; the sample size used was 364 participants

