1.9 ETHICAL CONSIDERATIONS

Ethical approval was sought from the School of Medicine Research and Ethics Committee (SOMREC).

Permission was sought from the Mulago Hospital Ethics committee.

Informed consent was sought from the study participants.

Confidentiality was observed throughout the study.

DATA COLLECTION TOOL

3.5 Pulse....../min.

INCIDENCE OF AND FACTORS ASSOCIATED WITH POST-OPERATIVE NAUSEA AND VOMITING AMONG PATIENTS UNDERGOING REGIONAL ANAESTHESIA

QUESTIONNARE 1 (to be completed by the principal investigator or research assistants) Study Number: Patient's name: **Pre-operative assessment** 1. Case details (state) 1.1 Diagnosis.... 1.2 Procedure..... 2. Urgency of Surgery (Tick one) 2.1 Elective 2.2 Emergency 3. Patient details (preoperative assessment as recorded) 18-30 31-50 3.1 Age (years) 3.2 Sex M 3.3 Weight.....kg. 3.4 ASA classification

3.6 BP.....

4. Patient experience		

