5.2 Time since the last feed (tick appropriately)		
2hrs 4hrs 6hrs	8hrs [>8hrs

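### Age, fasting time and duration of anaesthesia are recorded only as tick boxes, and the lowest-BP boxes cannot tell a normal value from a missing one, so tests of these covariates lose precision

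*Protocol*

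**What the plan says.** Protocol 1.8.2 lists age, period of pre-operative fasting, and duration of anaesthesia and of surgery among the independent variables. Protocol 1.8.4 states that "Continuous variables were expressed as means and standard deviations while categorical data was expressed as frequencies with their respective proportions". It also allows participant characteristics to be shown as categories, as continuous values or both. Each variable is then compared with the outcome by cross tabulation and logistic regression.

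The data collection tool captures these items as follows:

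- **Age** (Questionnaire 1, item 3.1): bands, of which two are visible, "18-30 31-50 3.1 Age (years".
- **Fasting** (Questionnaire 1): "5.2 Time since the last feed (tick appropriately", with boxes at 2, 4, 6, 8 and more than 8 hours.
- **Duration of anaesthesia and of surgery** (Questionnaire 2, items 2.2 and 2.3): boxes at 30, 30-60, 60-120 and over 120 minutes.
- **Surgery clock times** (Questionnaire 2, item 2.1): started and "ended (state in 24hour clock".
- **Lowest BP** (Questionnaire 2): "3.6.Lowest BP recorded(tick", with SBP boxes <110, <90, <50 and DBP boxes <90, <70, <50.

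Weight and pulse are written in as numbers on Questionnaire 1, and pre-operative BP appears to be as well.

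**The concern.** Objective 2 is about factors associated with PONV, so the way those factors are measured limits what it can show. There are two separate problems.

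**Loss of information.** Banding a continuous covariate discards the variation within each band. This weakens the test of that covariate and leaves residual confounding when it is used for adjustment.

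**Ambiguous boxes.** A 60-minute duration fits two bands. A fast of 3, 5 or 7 hours has no box, and the form gives no rounding rule. A lowest SBP of 85 satisfies two boxes, while one of 115 satisfies none. A blank can therefore be a normal reading or a missing one. If blanks were entered as missing and lowest BP went into a complete-case logistic model, the patients removed would be the normotensive reference group.

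**Working it through.** **1. The plan's own figures.** Protocol 1.5 sizes objective 2 on sex: "Using a level of significance of 5" per cent and "For a power of 80" per cent, with q1 = 0.554, q2 = 0.446, p1 = 0.065, p2 = 0.174 and P = 0.114.

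- First term: 1.96 × √[(1/0.554 + 1/0.446) × 0.114 × 0.886] = 1.96 × 0.639 = 1.253.
- Second term: 0.841 × √[0.065 × 0.935/0.554 + 0.174 × 0.826/0.446] = 0.841 × 0.657 = 0.553.
- N = (1.253 + 0.553)² / 0.109² = 274.5, against 272 stated. This reproduces to within 1%.

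Objective 1 ("Assuming an incidence of PONV in regional anaesthesia of 31.4" per cent): 1.96² × 0.314 × 0.686 / 0.05² = 331, and 331 × 1.10 = 364. This also reproduces.

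Power for the sex comparison is 79.7% at 272, 86.7% at 331 and 89.6% at 364. Sex is binary, so the tick bands do not touch these figures.

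**2. What can be recovered from the form.**

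| Item | Exact value on visible form? | Box problem |
|---|---|---|
| Age | No | Banded |
| Time since last feed | No | Single values, nothing in between |
| Duration of anaesthesia | No | 60 min in two bands |
| Duration of surgery | Yes, from item 2.1 | 60 min in two bands of item 2.3 |
| Lowest SBP and DBP | No | Nested; none for SBP ≥110 or DBP ≥90 |

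**3. Information kept by the bands.** The protocol gives no distributions for these covariates, so every input here is an assumption. Information kept = between-band variance / total variance.

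- Age: normal, truncated at 18, mean 32-45, SD 12-16, with one or two assumed bands above 50. Kept: 77-87%.
- Duration: log-normal, median 50-90 min, log-SD 0.5. Kept: 70-83% on the minute scale, 83-85% on the log scale.
- Lowest SBP: normal, mean 95-110, SD 15-18, with blanks correctly read as 110 or more. Kept: 76-80%.

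Fasting was not quantified.

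**4. Effect on power.** Take a covariate with 80% power if measured exactly, two-sided 5%, and a linear effect. Its expected z is 1.960 + 0.842 = 2.802. If a share r of the information is kept, power with a 1-df trend term is Φ(2.802√r − 1.960).

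| r | Trend, 1 df | Dummies, 2 df | Dummies, 3 df |
|---|---|---|---|
| 0.70 | 65% | 54% | 48% |
| 0.80 | 71% | 61% | 54% |
| 0.85 | 73% | 63% | 57% |
| 0.87 | 74% | 64% | 58% |

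The dummy columns use the noncentral chi-square with noncentrality 2.802² × r. The trend column assumes band scores proportional to band means. With equally spaced scores, the duration bands keep only 64-76% on the minute scale; at 0.644 trend power is 61%.

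**5. Cross-check by simulation.** Assumptions: age mean 40, SD 12, truncated at 18; a third band above 50; OR 1.4 per SD; n = 331; 1,500 fits; simulation error about one percentage point. At 31.4% incidence, power is about 80% with age in years, 70% with a trend over bands and 60% with dummies. At 11.4% incidence it is 51%, 43% and 34%.

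**6. Blank BP items.** Under the SBP assumptions in step 3, 16-50% of patients would never fall below 110. Of 331 patients that is 331 × 0.16 = 53 to 331 × 0.50 = 166 with no SBP box to tick.

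**The case against.** A reader might infer that the means and SDs planned in 1.8.4 are impossible. The documents do not support that. Surgery duration can be computed from item 2.1. The same section allows characteristics to be categorical, and no sentence promises a mean for age, fasting or BP specifically. Weight and pulse are numeric fields to which the sentence can apply.

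A reader might also infer that objective 2 as a whole loses power. It does not: its stated power rests on sex alone, and the protocol claims no power for age, fasting or duration.

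Other points against the concern have weight:

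- The size of the loss depends on assumed distributions, and a linear effect favours continuous coding. In the age simulation, about half of the fall from 80% to 60% comes from dummy coding, which the protocol does not specify.
- Lowest BP is not listed in 1.8.2, and nothing says that blanks are treated as missing or that it enters the multivariable model. Dropping normotensive patients is a risk, not a stated plan.
- The form was extracted imperfectly. Age boxes above 50 may have been lost, and the 30-minute box may have lost a less-than sign. Neither a missing age band nor an overlap at 30 minutes should be asserted.
- The protocol is in the past tense, with data collected from August 2018 to January 2019, so rewording the form cannot repair completed forms.

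These points narrow the finding but do not remove it. Three listed covariates still have no exact value on the visible form, 60 minutes still falls in two bands, and a blank BP item is still ambiguous.

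**Conclusion.** The point holds as a measurement weakness in several covariates. It is not a contradiction of the analysis section or an error in the sample size. The incidence estimate and the stated power for sex are unaffected.

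For covariates that are truly banded, a test with 80% power on exact values would have about 65-74% with a trend term and about 48-64% with 2-3 df dummies. These ranges rest on a linear effect and on 70-87% of the information being kept; the distributions behind that range are assumptions. The box defects (shared 60 minutes, fasting gaps, nested and incomplete BP boxes) are visible on the form and need no assumption. The change is worth making because it is cheap; it is not critical to the study's main result.

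**What to change.** **For any further use of the form.** Write in age in years, hours since last feed, anaesthesia start and end times, and lowest SBP and DBP in mmHg. Compute surgery duration from the item 2.1 times and drop the boxes in 2.3. Enter these as continuous terms in the logistic models and keep bands for descriptive tables only. Any bands that remain should be exclusive and exhaustive.

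**For forms already completed.** Use the item 2.1 times for surgery duration. Code an unticked lowest-BP item as not below 110/90 only where the chart confirms a reading; otherwise code it as missing. The form offers no way back to exact values for age, fasting or duration of anaesthesia. For these, state the coding used (trend or dummies) and how a 60-minute duration and in-between fasting times were assigned.

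**Cost.** Slightly more data entry on new forms, and some chart checking for completed ones. The sample size does not change.

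### The 24-hour PONV incidence is taken over completers only, so a recovery-room event in a patient later lost is dropped or miscounted, and all loss must be unrelated to PONV

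*Protocol*

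**What the plan says.** In section 1.8.4 the numerator of the cumulative incidence is everyone with PONV in the 24-hour window. The denominator is narrower, since that count is "divided by the total number of study participants enrolled into the study with complete follow up". The completeness condition is attached to the denominator, and complete follow-up is not defined.

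Section 1.8.3 defines the outcome as "any retching, nausea or vomiting within 24 hours following surgery under regional anaesthesia". Section 1.8.1 provides a single contact: "Patients were followed up once at 24 hours to assess for post-operative nausea and vomiting".

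Questionnaire 2 also captures the outcome earlier. Its recovery item ("5.1 Did any of the following happen during recovery") has yes/no ticks for retching, nausea and vomiting. The 24-hour block then asks about nausea or vomiting and, only if the answer is yes, for the "time to occurrence of PONV from time of surgery".

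Section 1.5 sizes Objective 1 for an absolute error of 0.05 and then enlarges the sample ("Adjusting for loss to follow up of 10" percent), reaching 364.

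**The concern.** Because any one episode is enough, a patient who retches, feels nauseated or vomits in recovery already has a positive outcome, whatever happens later. That patient can still lack the 24-hour contact and so fall outside the stated denominator. The rule does not say what happens then. If numerator and denominator are both limited to completers, a known case is discarded. If the completeness condition is applied only where it is written, the case enters the numerator but not the denominator, and the result is not a proportion of any one population.

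The rule also needs every loss, whether or not a recovery event came first, to be unrelated to PONV. This is the estimate for Objective 1, which set the final sample size. A confidence interval computed on completers reflects sampling error only and would not show an error from selective loss.

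**Working it through.** **The plan's own figures (section 1.5).** With z = 1.96, p = 0.314 and d = 0.05, N = 1.96² × 0.314 × 0.686 / 0.05² = 330.998, so 331. Then 331 × 1.10 = 364.1, so 364. Both reproduce.

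**Assumptions for the size of the effect.** 364 enrolled; 36 lost (10% of 364); 328 complete; 103 events among completers, 103/328 = 31.4%. The 10% is the planning allowance, not observed loss.

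**Incidence over all 364, by risk among the 36 lost:**

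- none had PONV: 103/364 = 28.3% (completers 3.1 points too high)
- half the risk, 0.157: (103 + 0.157 × 36)/364 = 108.65/364 = 29.8% (about 1.6 points too high)
- equal risk: 31.4% (no bias)
- double the risk, 0.628: (103 + 0.628 × 36)/364 = 125.61/364 = 34.5% (3.1 points too low)
- all had PONV: 139/364 = 38.2% (6.8 points too low)

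Taking 33 lost instead (364 − 331, with 104/331 = 31.4%) gives 28.6% to 37.6%, and 30.0% at half the risk.

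**Recovery events among the lost.** Let k of the 36 lost have a recorded recovery event (k is an assumption; the protocol gives no figure).

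| k | Dropped | Numerator only, (103+k)/328 | Added to both, (103+k)/(328+k) | Lower bound, (103+k)/364 |
|---|---|---|---|---|
| 5 | 31.4% | 32.9% | 32.4% | 29.7% |
| 10 | 31.4% | 34.5% | 33.4% | 31.0% |

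The upper bound stays at 139/364 = 38.2%. Adding only the known cases to both parts is not a remedy. It admits lost patients who had an event and leaves out lost patients who did not, which pushes the estimate up.

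**Two-step estimate.** Let N be all enrolled patients who had surgery under regional anaesthesia and r those with a recovery event. Let m be those event-free in recovery who were reached at 24 hours, and e the number of those m with an event. Then

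incidence = r/N + (1 − r/N) × e/m.

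Let c be the number of completers with a recovery event. The completer proportion is the same expression with c/(c + m) in place of r/N. The two therefore differ by [r/N − c/(c + m)] × (1 − e/m). The difference vanishes when the recovery-event share is the same in lost patients as in completers, and otherwise corrects for loss that depends on recovery status. Only the recovery ticks and the 24-hour answer are used.

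**The case against.** A 24-hour cumulative incidence over complete cases is conventional, and the more natural reading of section 1.8.4 is completers over completers; the numerator-only reading is literal but strained. Dropping known events is not in itself a bias: if loss is unrelated to PONV, only precision suffers. Both points stand. The rule remains unclear, and the condition on loss is wider than the collected data require.

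Complete follow-up might also mean that the outcome has been ascertained, since section 1.7 speaks of follow-up lasting up to 24 hours. A recovery event would then count in both parts. The text does not say this, and that version gives the upward-biased figures in the fourth column of the table.

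Sensitivity analyses are commonly left to a statistical analysis plan, which is not shown. Their absence is therefore not the charge; the fault lies in a denominator that the protocol itself fixes.

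Three stronger readings might be inferred, and the documents do not support them.

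- *That the error matches the planned ±5 points.* Downward it cannot exceed 3.1 points under the assumptions above. Upward, 5 points needs 0.364 × 364 − 103 = 29.5 of the 36 lost, or 82%, to have had PONV.
- *That a Kaplan-Meier analysis of the recorded times would resolve it.* The time item follows a yes at 24 hours, so lost patients have none. The recovery item shows only ticks, and no recovery-discharge time is visible (part of that page is not shown). Censoring would also still assume that later loss is unrelated to PONV.
- *That patients who leave early differ in risk.* The protocol describes no such patients.

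**Conclusion.** The concern holds in moderate form. The written rule can discard or miscount a known case, and it relies on all loss being unrelated to PONV when the recovery data would allow a weaker condition. At an assumed 36 of 364 lost, a halved risk among the lost shifts the estimate by about 1.6 points and a doubled risk by 3.1 points. The range 28.3% to 38.2% is a pair of limits, not an expectation. These figures rest on the 10% planning allowance and the assumed 31.4%. With admitted patients and one contact at 24 hours, true loss may be well below 10%, and the effect would shrink in proportion. The number of recovery events among lost patients is unknown. The point is worth correcting because it concerns the estimate for Objective 1 and uses data the form already collects.

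**What to change.** In section 1.8.4, use one population for numerator and denominator: enrolled patients who had surgery under regional anaesthesia. State that a recorded recovery-room event settles the outcome whether or not the 24-hour contact takes place. Estimate incidence by the two-step formula above, with a confidence interval that reflects both steps, for example by bootstrap.

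Beside it, report the completer proportion, the number lost before 24 hours (split by recovery event), and best/worst-case bounds over the whole population. The bounds are needed because the two-step estimate still assumes that loss after recovery is unrelated to later PONV.

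The cost is a change of wording and slightly more analysis. No event times and no new data are required. The remaining assumption about loss is narrower than before but does not disappear.
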